10.5 Procedures for Reporting AEs and SAEs

Spontaneous reporting of adverse events will be recorded in the PPD app and reported appropriately. Care will be taken not to introduce bias when questioning a subject about any changes in their health. Participants will have the ability to report changes to their health via the app through the Health Change Form or chat. Participant may also choose to communicate with the virtual site study team via email or phone call to report a change to their health. Upon reporting of health change by the participant through these methodologies, study doctor or designee will be alerted to reach out to the participant to follow-up for a possible adverse event and document their findings within the PPD study portal.

Each AE is to be assessed by the virtual PI to determine if it meets the criteria for a SAE. If a SAE occurs, expedited reporting will follow local and international regulations, as appropriate.

The AEs/SAEs will be recorded within PPD app. It is not acceptable for PPD to share any subject's medical records to GSK CH in lieu of completion of the AE form.

In addition to the subject recording the event on the PPD app, all SAEs will be reported to Case Management Group (CMG), Global Safety at GSK CH (GSK CMG).

Following completion of the subject AE page within PPD app, PPD medical qualified person will review the self-reported information and assess if the AE meets the definition of an SAE. PPD will enter available information into the SAE form and will forward the completed SAE form to GSK CMG within 24 hours of receiving the questionnaire data.

If additional details are required from the subject in order to determine if the reported AE meets SAE criteria, PPD will re-contact the subject to query the AE details. If it is not possible to re-contact the subject within 24 hours, PPD will complete the SAE form to the extent possible with the available information and will send to GSK CMG within the 24 hour time will contact the subject on a further 3 occasions to attempt to collect further details and will share additional information with GSK CMG.

All collected SAE-related data should be sent to GSK CMG PPD , GSK CH Clinical Operations Safety Reporting email box PPD and the GSK clinical study manager associated with the present study.

Protocol Number: 216953

In order to maintain compliance with international and national regulatory bodies, the subject will be notified in the eIC that they may be further contacted in order to collect additional information required to evaluate the potential event.

AEs/SAEs will be reported to local and regional health authorities by GSKCH, when appropriate, in accordance with applicable local and regional regulations. Prompt notification of SAEs by PPD to GSKCH is essential so that legal obligations and ethical responsibilities towards the safety of subjects are met.

GSKCH will comply with country specific regulatory requirements relating to safety reporting to the regulatory authority, IRB/EC, etc. Both PPD and GSKCH will comply with all local medical device reporting requirements Safety reports must be prepared for suspected unexpected serious adverse reactions (SUSAR) according to local regulatory requirements and sponsor policy.

10.6 Procedures for Reporting HSI

HSI will be monitored on social media during subject recruitment. If PPD identifies HSI in comments/posts under advertisement material which relate to subject participation to the study, PPD is responsible to ensure the HSI will be submitted using reporting form provided by GSKCH within 24 hours of awareness (or next working day if over a weekend) via a secure email or fax to:

		Email address	S. PPD						
			Fax: PPD						
GSK	CMG	PPD		and	the	GSK	clinical	study	manager
assoc	iated w	ith the present study will	be copied in the	e ema	il.				
		- :		4 41		NT			A.T.

PPD is responsible to retain record that the HSI was sent/received for AE reconciliation at the end of the study.

10.7 Procedure for reporting AEs after study completion

The study subjects will be allowed to retain unused products after completing the study. Subjects will be asked to remove the study label from the toothpaste tubes and they will be asked to report any issues/questions or comments as per commercial tube instructions.

10.8 Withdrawal Due to an Adverse Event

Withdrawal due to AEs should be distinguished from withdrawal due to other causes, according to the definition of an AE noted earlier, and recorded on the appropriate AE eCRF (PPD app) page.

When a subject withdraws because of an SAE, the SAE must be reported in accordance with the reporting requirements defined.

10.9 Pregnancy

For GSK CH studies in which no drug is utilized or studies of single-use marketed products that are classified as a non-medicinal product in the market where the testing is occurring and there is no pregnancy warning on labelling, a pregnancy test will not be required and it will not be an exclusion criteria for this study. Pregnancy information will be collected only for spontaneous pregnancy reports.

Property of GSK Consumer Healthcare - Confidential

May not be used, divulged, published or otherwise disclosed without the consent of GSKCH

SOP-208661 Clinical Protocol Template v6.0

Protocol Number: 216953

10.9.1 Action to be Taken if Pregnancy Occurs

PPD will record pregnancy information on the appropriate form and e-mail it to the GSK CH Clinical Operations Safety Reporting email box PPD within 24 hours of learning of the subject becoming pregnant. The GSK CH Study Manager or designee will be responsible for forwarding the pregnancy form to the Case Management Group, Global Safety mailbox PPD

The subject will be followed to determine the outcome of the pregnancy. Information on the status of the mother and infant / neonate (including concomitant medications taken by the mother during the pregnancy) will be forwarded by PPD to the GSK CH Clinical Operations Safety Reporting email box and the GSK CH Study Manager or designee will forward this information to the Case Management Group, Global Safety group mailbox at GSK PPD . Generally, follow-up will be no longer than 6 to 8 weeks following the estimated delivery date. Any termination of the pregnancy will be reported. While pregnancy itself is not considered to be an AE, abnormal pregnancy outcomes (e.g. spontaneous abortion, fetal death, stillbirth, congenital anomalies, ectopic pregnancy) are, and should be recorded as an SAE.

11 DATA MANAGEMENT

As used in this protocol, the term eCRF is understood to refer to an electronic data record (PPD portal).

For this study, subject data will be entered into the PPD app, a validated system. Data relating to SAEs and pregnancy will also be collected on specific forms.

PPD is responsible for verifying that data entries are accurate in the eCRF.

Each subject will be assigned and identified by a unique Screening Subject Number. Any reference made to an individual subject within the study must be done using their unique Screening Subject Number.

11.1 Case Report Form

A CRF is a printed, optical, or electronic document designed to record the protocol required information to be reported to the sponsor on each trial subject.

For each subject who has given informed consent the eCRF (PPD portal) must be completed and reviewed for completion and accuracy. PPD must maintain accurate documentation that supports the information entered in the eCRF.

Management of clinical data will be performed in accordance with PPD applicable standards and data cleaning procedures with oversight by GSK CH to ensure integrity of the data, for example, to remove errors and inconsistencies in the data.

To protect the privacy of subjects, no Personally Identifiable Information (PII) (including the subject's name or initials or full birth date) is to be recorded in the eCRF or as part of the query text.

Data collection, processes as outlined in PPD processes and SOPs will be documented via Data Management Plan.

Clinical Protocol

Protocol Number: 216953

All eCRF (PPD portal) pages should be completed by subjects when the eCRF has been designated as the source.

GSK CH will obtain and retain all eCRFs and associated study data as applicable at the completion of the study.

11.2 Data Handling

Documentation of all data management activities should allow step-by-step retrospective assessment of data quality and study performance.

Any changes or corrections to data will be performed in the Electronic Data Capture (EDC) System, PPD app, and it will include rationale for changes. The EDC system has an audit trail, which will provide a complete record of the changes and corrections endorsed by PPD

Adverse events will be coded using Medical Dictionary for Regulatory Activities (MedDRA) and any concomitant medications terms (if applicable) using an internal validated medication dictionary, COL

11.2.1 Data Queries

The PPD data management team will perform edit checks as the data are being entered into the system, and queries will be entered on a data issues log for the decentralized site staff to address. The Clinical Dictionary Development and Management Group will raise queries as needed on safety data to code the terms (AEs and Drugs or concomitant medication) appropriately.

11.3 Processing Patient Reported Outcomes

Electronic Patient reported outcome (ePRO) data will be collected using electronic devices and transferred electronically to GSKCH or PPD

To protect the privacy of subjects, no PII (including the subject's name or initials or birth date) is to be recorded on any PRO/ePRO that will be forwarded to GSK CH or PPD

12 STATISTICAL CONSIDERATIONS AND DATA ANALYSES

12.1 Sample Size Determination

No formal sample size calculation has been performed for this study however sufficient subjects will be screened (estimated screen failure 50%) to have approximately 650 subjects enrolled and 400 completers (estimated 40% drop-out).

There is no prior information for the use of DHEQ in DH sufferers in a RWE setting. It is believed that for this study 400 subjects are deemed sufficient to observe a trend over time from baseline at 24 weeks in total score.

12.2 Populations for Analysis

The Screened population will include subjects who sign the eIC and enter the screening process of assessment of inclusion and exclusion criteria.

Clinical Protocol

Protocol Number: 216953

The Enrolled population will include all subjects who meet the inclusion/exclusion criteria and identified by the screening questionnaire

The Safety population will include all subjects who receive at least one dose of study product. Safety population will be used of safety variables.

The modified Intent-To-Treat (mITT) population will include all subjects who receive at least one dose of study product and have at least one post baseline DHEQ-48 questionnaire data. Efficacy data will be summarized using the mITT population only.

12.3 Sub-Group classification

A total of 4 different groups will be identified at screening for the purposes of sub-group analyses:

- Age group
 - $\circ \le 40$ years old
 - \circ > 40 years old
- Diagnosis
 - o self-reported DH without previous diagnosis by a dentist
 - o self-reported DH with previous diagnosis by a dentist
- Use of sensitivity toothpaste
 - o Non-users will include subjects who are not currently using a sensitivity toothpaste e.g. first-time user
 - o Intermittent users will include subjects who sometimes use a sensitivity toothpaste
 - o current users will include subjects who regularly (daily) use a sensitivity toothpaste
- Self-reported DH frequency
 - o frequent = Several times a day, Once a day, Several times a week
 - o less frequent = Once a week, Several times a month, once a month, less than once a month

12.4 Statistical Analyses

Additional details of the proposed statistical analysis will be documented in the statistical reporting and analysis plan (RAP), which will be written following finalization of the protocol and prior to study analysis (as appropriate). This section is a summary of the planned statistical analyses including primary and exploratory endpoints. Additional details for exploratory endpoints will be further described in detail in the RAP.

12.4.1 Primary Analysis

For the primary objective, plots of the mean values for section 1 questions Q1-3, and questions in section 2 for total DHEQ score – section 2 (sum Q1-34), each of the domain's mean values (Restrictions – sum Q1-4, Adaptation – sum Q5-16, Social Impact – sum Q17-21, Emotional Impact – sum Q22-29, Identity – sum Q30-34), Global oral health (Q35) and Effect on life overall (sum Q36-39) will be presented over 24 weeks to assess QoL over time in the overall population of DH sufferers, graphically.

GSK Consumer Healthcare

Clinical Protocol

Protocol Number: 216953

12.4.2 Safety Analyses

All AEs will be coded using MedDRA. AEs will be categorized as oral and non-oral by prior to database lock. The number of AEs/SAEs and number of subjects with AEs/SAEs will be listed and tabulated.

12.4.3 Other Analyses

The exploratory endpoints will be analyzed as follows. Further details will be provided in the RAP.

Plot over time in DHEQ mean scores for each sub-group

For the exploratory objective relating to sub-groups, plots of the mean values for section 1 questions Q1-3, and questions for section 2 total DHEQ score – section 2 (sum Q1-34), each of the domain's mean values (Restrictions – sum Q1-4, Adaptation – sum Q5-16, Social Impact – sum Q17-21, Emotional Impact – sum Q22-29, Identity – sum Q30-34), Global oral health (Q35) and Effect on life overall (sum Q36-39) will be presented over 24 weeks to assess QoL over time in the further characterisation of DH sufferers by sub-group classification, graphically.

 DHEQ Mean scores over time compared to baseline (0, 4, 8, 12, 16, 20 and 24 weeks) to be analysed for overall DH sufferers and each sub-group

The exploratory response variable is the DHEQ mean score at 0, 4, 8, 12, 16, 20 and 24 weeks respectively in total score, each of the DHEQ domain scores, questions Q1-3, Global oral health and Effect on life overall.

An Analysis of Variance (ANOVA) model will be used to analyze the DHEQ score as the response variable and timepoint as the dependent variable. Subject will be included as a random effect. Each post baseline timepoint will be compared to baseline using the adjusted means from the time variable from the model.

For the analysis of the 4 subgroups, an extra factor for the subgroup will be included along with the subgroup*timepoint interaction. This will enable to look at the differences between subgroup and the interaction term will enable adjusted means of each subgroup over time.

For the ANOVA if the underlying assumptions are not met, alternative methods will be sought, including transformations or non-parametric methods.

 Percentage of DH sufferers who agree (score 5-7) to items in each respective domain at baseline and week 24

A table for percentage of consumers who agree (score 5-7) to items in each domain at baseline and at week 24 respectively will also be presented as part of this objective

 Numeric Pain Rating Scale (NPRS) Mean scores over time compared to baseline (0, 4, 8, 12, 16, 20 and 24 weeks) to be analysed for overall DH sufferers and each sub-group

The exploratory response variable is the NPRS mean score at 0, 4, 8, 12, 16, 20 and 24 weeks. An Analysis of Variance (ANOVA) model will be used to analyze the NPRS score as the response variable and timepoint as the dependent variable. Subject will be included as a random effect. Each post baseline timepoint will be compared to baseline using the adjusted means from the time variable from the model.

GSK Consumer Healthcare

Clinical Protocol

Protocol Number: 216953

For the analysis of the 4 subgroups, an extra factor for the subgroup will be included along with the subgroup*timepoint interaction. This will enable to look at the differences between subgroup and the interaction term will enable adjusted means of each subgroup over time.

For the ANOVA analyses if the underlying assumptions are not met, alternative methods will be sought, including transformations or non-parametric methods.

A plot over time in NPRS mean scores will also be presented along with a table reporting the percentage of participants who achieve pain reduction identified as clinically important (pain reduction NPRS > 30%)

• Satisfaction Numerical rating scale (NRS)

The satisfaction Numerical rating scale will be summarized using frequencies at week 24. Similar summaries will be presented for overall population and each of the subgroups.

• Oral hygiene habits of DH sufferers according to oral hygiene questionnaire

A summary of oral hygiene habits at baseline will be provided as part of this objective

12.4.4 Exclusion of Data from Analyses

Exclusion of any data from the analyses will be determined during a data review meeting prior to database lock and pre-defined in the RAP. Any reasons for exclusion from an analysis population will be listed, if applicable. As there is no PP analysis planned, only an assessment of subjects being in the safety and mITT populations will be made.

12.4.5 Demographic and Baseline Characteristics

Age and other continuous demographic and baseline variables will be summarized using descriptive statistics such as mean, range, median and standard deviation. Gender, race, ethnicity and other categorical demographic and baseline variables will be summarized using frequency counts and percentages for the safety and mITT populations.

12.4.6 Study Product Compliance and Use of Other Therapies

12.4.6.1 Study Product Compliance

Study product compliance and compliance to the study schedule will be tabulated and summarized for the safety population.

Summaries will include a simple yes/no frequency (and percent) count at each timepoint:

- Summary of completion to study schedule and assessments (yes/no)
- Summary of product usage according to product instructions (yes/no)
- Summary of number of tubes remaining at the end of the study (number remaining)

12.4.6.2 Prior and Concomitant Medications

Concomitant medications taken during the study will be listed for the safety population.

Protocol Number: 216953

12.4.7 Handling of Dropouts and Missing Data

Missing data due to general dropout/withdrawals will be assessed on an ongoing basis during the study. Any further sensitivity analyses needed due to missing data will be reviewed at the time of data review.

For the DHEQ data, for any timepoint if response is missing will be excluded from the primary analysis however the data available for each subject (even though some time points may be missing) will still be included in the analysis.

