1.2 Schedule of Activities

The schedule of activities table provides an overview of the study.

Table 1-1 Schedule of Activities

Procedures	Screening	Baseline* Week 0 (Day 0)	Week 4 Day 28 (± 7 days)	Week 8 Day 56 (±7 days)	Week 12 Day 84 (±7 days)	16 Day 112	20 Day 140	Week 24 Day 168 (± 7 days)
Electronic Informed Consent	X							
Demographics	X							
Inclusion/exclusion criteria	X							
Screening questionnaire	X							
Subject eligibility	X							
Medical History ¹	X	X						
Concomitant Medications		X	X	X	X	X	X	X
DHEQ-48 completion		X	X	X	X	X	X	X
NPRS scale		X	X	X	X	X	X	X
Oral Hygiene questionnaire		X						
Study product shipped [dentifrice] ²		X						
Patients' satisfaction with treatment (NRS)								X
AEs ³	X	X	X	X	X	X	X	X
Study Conclusion								X

Abbreviations:

216953 | Protocol clinical protocol 08 Jul 2022 | TMF-194147 | 2.0

GSK Consumer Healthcare Clinical Protocol

Protocol Number: 216953

AEs: Adverse Events

DHEQ: Dentin Hypersensitivity Experience Questionnaire

NRS: Numerical Rating Scale NPRS: Numeric Pain Rating Scale

Footnotes

- ¹ Medical occurrences and AEs which subjects experience from the time of consent signature, but prior the use of the study product, will be recorded in the Medical History
- ² Product will be shipped only after baseline assessments have been completed
- ³ Any events experienced from the first use of the product until last administration of the study product will be recorded as AEs. All serious AEs (SAEs) will be collected immediately after a subject provides consent signature until last administration of the study product.
- * Baseline activities must be conducted within 14 days from subject eligibility

Protocol Number: 216953

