8 STUDY PROCEDURES

This section lists the procedures to be completed at each planned study time point. However, as per nature of RWE studies, if a subject fails to complete DHEQ-48 questionnaire or NPRS scale at any timepoint post baseline, subject will be permitted continuing in the study.

The timing of each procedure is listed in the Schedule of Activities.

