## Statistical Analysis

## 4.1 Sample Size Calculation

No formal sample size calculation has been performed for this study however sufficient subjects will be screened (estimated screen failure 50%) to have approximately 650 subjects enrolled and 400 completers (estimated 40% drop-out).

There is no prior information for the use of DHEQ in DH sufferers in a RWE setting. It is believed that for this study 400 subjects are deemed sufficient to observe a trend over time from baseline at 24 weeks in total score.

PPD	GSK-001 SAP	
	Page 9 of 14	Version
	70114	1.0

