## 4.3 Analysis

### 4.3.1 Population to be Analyzed

The Screened population will include subjects who sign the eIC and enter the screening process of assessment of inclusion and exclusion criteria.

The Enrolled population will include all subjects who meet the inclusion/exclusion criteria and identified by the screening questionnaire

The Safety population will include all subjects who receive at least one dose of study product. Safety population will be used of safety variables.

PPD	GSK-001 SAP	
ווט	Page 10 of 14	Version 1.0

The modified Intent-To-Treat (mITT) population will include all subjects who receive at least one dose of study product and have at least one post baseline DHEQ-48 questionnaire data. Efficacy data will be summarized using the mITT population only.

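### The primary DHEQ curve averages whoever answered at each visit, so with about 40% expected drop-out it can move without any true change, by an amount and in a direction the documents do not give

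*Protocol*

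**What the plan says.** - **Primary result.** Protocol 12.4.1 and SAP 4.3.6 define plots of mean DHEQ values that "will be presented over 24 weeks to assess QoL over time in the overall population of DH sufferers, graphically". Neither names a model. Adjusted means appear only in the exploratory ANOVA (Protocol 12.4.3, SAP 4.3.7.3), so reading the primary means as unadjusted is an inference, though a natural one.
- **Missing visits.** Protocol 12.4.7, repeated in SAP 4.3.8, says "for any timepoint if response is missing will be excluded from the primary analysis however the data available for each subject" is retained. Protocol 8 adds that "if a subject fails to complete DHEQ-48 questionnaire or NPRS scale at any timepoint post baseline, subject will be permitted continuing in the study".
- **Expected loss.** SAP 4.1 plans for "approximately 650 subjects enrolled and 400 completers (estimated 40% drop-out". Protocol 12.1 holds that "400 subjects are deemed sufficient to observe a trend over time from baseline at 24 weeks in total score".
- **Population.** Under SAP 4.3.1, mITT members must have had a dose and "have at least one post baseline DHEQ-48 questionnaire data. Efficacy data will be summarized using the mITT population only". Protocol 12.2 says the same.
- **Existing safeguards.** SAP 4.3.7.3 plans an ANOVA with subject as a random effect, comparing every visit with baseline. SAP 4.3.8 plans multiple imputation by fully conditional specification (FCS), but only for secondary and exploratory analyses. It ties imputation to a missing-at-random judgement made by comparing demographics. Protocol 12.4.7 leaves further sensitivity analyses to data review. Completion by timepoint is tabulated (Protocol 12.4.6.1, SAP 4.3.4), but nothing places it beside the primary plot.

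**The concern.** The week 24 mean comes from those who answered at week 24, and the week 0 mean from the whole mITT set. If leavers and stayers differ in DHEQ score, the two means differ even when nobody changes. In a single-arm study the primary figure has no second curve against which to see this.

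The objective is descriptive, but what it describes is subjects' quality of life over 24 weeks, and the sponsor expects a trend in the total score. A shift in who is being averaged would look like such a trend, or could hide one.

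The mITT rule adds a second selection. Subjects who leave before any post-baseline questionnaire are absent from the whole curve, baseline point included.

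**Working it through.** **1. The plan's own figures.** 400 / (1 - 0.40) = 667, against 650 enrolled. In reverse, 650 x 0.60 = 390 against 400, and 1 - 400/650 = 38.5%. These agree to within rounding. The 40% is of enrolled subjects, so the share missing at week 24 within mITT can be lower.

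**2. Size from first principles.** For a fixed starting group with no within-subject change, the shift in the raw mean is -d x g. Here d is the share missing at week 24 and g is the leavers' mean minus the stayers' mean, in SD units. The documents do not give g. With d = 0.385:
- g = 0.10: -0.04 SD
- g = 0.25: -0.10 SD
- g = 0.50: -0.19 SD
- g = 0: no shift; negative g reverses the sign

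The standard error of a mean of 400 is 1/sqrt(400) = 0.05 SD.

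**3. Simulation. All inputs below are assumptions.** 650 subjects with a baseline, 7 visits, SD 40, between-visit correlation 0.75 falling to 0.50, no true change, 40% lost by week 24. Drop-out depends on the last observed score with log-odds 0.1/0.3/0.6 per SD, higher scorers leaving. Entries are week 24 minus week 0 in total-score points; Monte Carlo error is about 0.1.

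| Share in mITT (lost before week 4) | Raw mITT plot | FCS imputation plus ANOVA, mITT |
|---|---|---|
| 93%, even loss (6.7%) | -1.06 / -2.89 / -5.20 | +0.24 / +0.52 / +0.68 |
| 84% (16%) | -0.50 / -1.42 / -2.95 | +0.10 / +0.79 / +1.81 |
| 75% (25%) | -0.09 / -0.16 / -0.37 | +0.36 / +1.55 / +2.89 |
| 68% (32%) | +0.35 / +0.94 / +1.75 | +0.70 / +1.67 / +3.51 |

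Two effects oppose each other. Later drop-out of high scorers pulls the raw curve down. Early loss leaves an mITT set with a low baseline, which then drifts back up. At 75% they nearly cancel. With log-odds -0.6 (lower scorers leaving) the raw column becomes +5.41, +3.01, +0.37 and -1.81.

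For scale, the standard error is 40/sqrt(400) = 2.0 points. If items score 1 to 7 (lower end assumed), the total spans 34 x 6 = 204 points.

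**4. Which analysis removes it.** With FCS imputation plus ANOVA on all subjects with a baseline, the largest residual in any timing is 0.22 points. An unstructured-covariance fit on that set gives the same. The random-subject model without imputation leaves up to +1.24 there, and +3.60 on mITT (68%, log-odds 0.6). Most of that residual comes from the mITT restriction.

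**5. The Safety population is not quite the same set.** Product ships after baseline and first use is confirmed separately (Protocol 6.2), so a subject can complete baseline and never use the product. If half the loss before week 4 comes before first use (assumed), the fit on the Safety population leaves about +0.6 to +1.4 points at log-odds 0.6. Another way of simulating that split gave +0.9, +1.4 and +1.8 at 84%, 75% and 68%. In the 75% case this is further from zero than the raw plot.

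**6. Other assumed patterns.**
- 400 finish but only 550 have a baseline, even loss: raw -0.6 to -3.6. With 500: -0.4 to -2.5.
- Skipped visits only, 10% rising to 40%: raw -1.0 to -6.4.
- Drop-out driven by the unseen score, even loss: raw -1.09/-3.64/-6.86. The unstructured fit on all with a baseline still leaves -0.30/-1.30/-2.67.

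**7. The imputation condition.** A demographic comparison says nothing about whether missingness depends on DHEQ. Adding baseline DHEQ to the same test would make matters worse: completers and non-completers would differ at p < 0.05 in 91-95% of simulated trials at log-odds 0.3, and in all of them at 0.6. The rule would then stop supporting imputation when it is most needed.

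**The case against.** The endpoint is defined as a plot, the objective is to describe, and there is no formal sample size calculation. SAP 4.3.7.3 already reports adjusted means for the same scores at every visit. In a simpler simulation with constant correlation 0.6, the raw plot moved by 0.14 SD either way while the random-subject model moved by only 0.02 SD (0.02 x 40 = 0.8 points). Completion counts are tabulated. Every size above is assumed, and one timing gives almost no shift. On this view the matter is one of presentation.

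Part of this stands. The plan does not ignore missing data, the sizes are illustrations, and a model-based headline is a choice with its own assumption. But the safeguards do not reach the primary figure, and their restriction to mITT matters. They reduce the shift when loss is spread out. When early loss is heavy they can end further from zero than the raw plot (75% and 68% rows).

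Three stronger readings are tempting, and the documents support none of them:
- That the curve will show a false improvement. The documents give no SD, no drop-out pattern and no difference between leavers and stayers, so neither size nor sign follows.
- That moving the model to the Safety population removes the problem. The residual within about 0.2 points was shown for all subjects with a baseline.
- That a corrected curve would show a product effect. There is no control arm.

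**Conclusion.** The concern holds as a statement about mechanism: an available-case plot in mITT, with about 40% expected loss and skipped visits allowed, can move because of who remains. Confidence in this is high.

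Confidence in the size is moderate. Under the assumed inputs the raw week 24 shift runs from about -5 to +2 points when higher scorers leave, with signs reversed when lower scorers leave. It is near zero for some timings, and absent if missingness is unrelated to score. The larger values exceed the 2.0-point standard error but are small against a 204-point span. The repair rests on missing-at-random; if drop-out depends on unseen scores, part of the shift remains. This is a cheap improvement, not a flaw that invalidates the study.

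**What to change.** 1. **Main figure (Protocol 12.4.1, SAP 4.3.6).** Show adjusted means with 95% confidence intervals from the repeated-measures model of SAP 4.3.7.3. Keep the observed means beside it as a labelled supportive plot, and print the number observed at each visit.
2. **Population (Protocol 12.2, SAP 4.3.1).** Fit the model to all subjects with a baseline DHEQ, without requiring a post-baseline value. If the curve is meant to describe product users only, use the Safety population: "The Safety population will include all subjects who receive at least one dose of study product", and its members should have a baseline because "Product will be shipped only after baseline assessments have been completed". In that case, state that a residual remains if score-related loss occurs before first use. Either way, amend the sentences that confine efficacy summaries to mITT, or the documents will contradict themselves.
3. **Imputation (SAP 4.3.8).** Delete the condition that rests on the demographic comparison. Use FCS imputation with DHEQ at all visits in the model, or an unstructured-covariance likelihood fit, under a stated missing-at-random assumption whatever that comparison shows. Impute at one stated level, for example domain scores with the total derived as their sum, so that total and domains stay consistent.
4. **Description.** Tabulate baseline DHEQ for week 24 completers and non-completers, as description and not as a condition for any analysis.
5. **Sensitivity (Protocol 12.4.7, SAP 4.3.8).** Pre-specify one analysis of the total score that shifts values after drop-out by an amount in both directions, over a range the sponsor chooses. The week 24 mean moves by the shift times the missing fraction. With an illustrative 10 points and 400 finishing, that is 10 x 250/650 = 3.8, 10 x 200/600 = 3.3, 10 x 150/550 = 2.7 or 10 x 100/500 = 2.0 points if 650, 600, 550 or 500 have a baseline.

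**Cost.** No new data and no new type of model; one extra table, one sensitivity analysis and a little more analysis work. The price is a headline figure that is model-based and depends on missing-at-random.
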